7.2 Sample Size and Power

7.2.1 Primary Cohort Sample Size and Power

As described in Section 4, we will recruit about 397 clinics—55% with a nursing/medical and 45% with medical/social care coordination model—to participate in this study. Although we recognize that we may not fully reach it, our goal is to recruit 100% of these clinics to participate in our study. All of these clinics will be eligible to contribute to our Primary Cohort analysis. Exact numbers of eligible patients from each clinic remains unknown, but we estimate that over a 12-month accrual period (01/01/2021 to 12/31/2021), each clinic will be able to contribute 57 patients on average. Among these patients, we estimate about 45%, or 26 patients per clinic, will be covered by one of our participating health insurance plans that will be contributing utilization outcomes. In addition, we have budgeted to survey 7,000 patients with an expected response rate of at least 60%, which would correspond with about 10 or 14 patients per clinic with 100% or 75% clinic recruitment, respectively.

Figure 4 illustrates the differences in outcomes we will be powered to detect under a range of clinic participation rates (i.e., 75%, 90%, and 100%) and number of eligible patients per clinic (ranging from 10-50). Power and sample size analyses were conducted using PASS (v.19) software, assuming two-sided tests ($\alpha=0.05$) with 80% power and an intra-cluster correlation of 0.01. For the composite care quality score, all scenarios indicate sufficient power to detect a difference in the percentage of quality measures at goal (range 0-100%) of at least 1%. For the primary utilization outcome, most scenarios indicate power to detect at least a 10% difference in the number of hospitalizations and inpatient visits. For the primary patient-reported outcome, all scenarios indicate the ability to detect at least a 1 point difference in the PROMIS-10 Global Health score (mean=50, standard deviation=10). Thus, we feel confident in our plan with this adaptation to achieve sufficient power to discover meaningful differences between care coordination models across all of our primary outcome measures for the Primary Cohort.

Figure 4: Power analysis for Primary Cohort

[figure not shown]
7.2.2 Historical Cohort Sample Size and Power

Among the 397 clinics we are recruiting for this study, 329 should be eligible to contribute patients to our Historical Cohort analysis. Exact numbers of eligible patients from clinic remains unknown, but we estimate that over a 14-month accrual period (01/01/2018 to 02/28/2019), each clinic will be able to contribute 66 patients on average. Among these patients, we estimate about 45%, or 30 patients per clinic, will be covered by one of our participating health insurance plans that will be contributing utilization outcomes.

Figure 5 illustrates the differences in outcomes we will be powered to detect under various scenarios for the Historical Cohort. Power and sample size analyses were conducted using PASS (v.19) software, assuming two-sided tests ($\alpha=0.05$) with 80% power and an intra-cluster correlation of 0.01. For the composite care quality score, all scenarios indicate sufficient power to detect a difference in the percentage of quality measures at goal (range 0-100%) of at least 1%. For the primary utilization outcome, most scenarios indicate power to detect at least a 10% difference in the number of

hospitalizations and inpatient visits. Thus, we feel confident in our plan with this adaptation to achieve sufficient power to discover meaningful differences between care coordination models across all of our primary outcome measures for the Historical Cohort.

Figure 5: Power analysis for Historical Cohort

7.3 Analysis Plan

7.3.1 Aim 1 Analysis

To evaluate the impact of coordination type (medical/social vs. nursing/medical) on study outcomes, we will specify a series of generalized linear mixed models (GLMMs). Individual patients (nested within clinic and organization) are the primary unit of analysis. To account for patient clustering, we will incorporate a random intercept for clinic into the model. Covariates will be specific to a given model (outcome) and will be selected based on a combination of substantive knowledge, empirical evidence, and model fit statistics (e.g., Bayesian Information Criterion). Investigators will first select a set of covariates that must be included in each model. From this initial set, a forward stepwise selection algorithm will select additional covariates to include until a stopping criterion is met, and the final model specification for each outcome is identified.⁵² Random effects will be evaluated and retained in a given model based on model fit statistics and Wald tests for covariance parameters. Patient care quality outcomes for Aim 1 analyses will be modeled as binary dependent variables (e.g., meeting goal vs. not meeting goal) within subgroups based on a patient's status at the time of care coordination initiation (e.g. meeting criteria at the start of care coordination vs. not), and corresponding GLMMs will have the general form:

$$(1) \eta_{ijk} = \gamma_{000} + u_{0j0} + \gamma_{100}X_{ijk} + \gamma_{010}CC_{jk} + \gamma_{020}W_{jk} + \gamma_{001}Z_k + \varepsilon_{ijk}$$

where η represents the log-odds of a care quality outcome (e.g., BP control); γ_{000} is the intercept (value for a 'typical' patient at a 'typical' clinic); u_{0j0} is the random intercept at the clinic level; X_{ijk} is a vector of covariates (age, etc.) for patient i within clinic j and organization k ; CC_{jk} represents the exposure variable of interest, care coordination type, designated at the clinic level; W_{jk} is a vector of clinic-level covariates; and Z_k is a vector of organization-level covariates. Effect estimates will be calculated via γ coefficients (specifically γ_{010} for the relative log-odds comparing the medical/social vs. nursing/medical care coordination model); ε_{ijk} is an error term. In addition to analyses of individual care quality

outcomes, we will also evaluate a composite outcome representing the proportion of applicable care quality outcomes that are met by a given patient. We intend to primarily evaluate this proportion as a continuous variable in a linear or tobit regression model that follows the structure in equation (1) above with the inclusion of a patient's baseline composite outcome as a covariate. However, based on the empirical distribution, we may also evaluate transformations to binary or multilevel categorical versions of this outcome as warranted.

Utilization outcomes for Aim 1 analyses will be evaluated both as binomial (any occurrence vs. none) and as counts. GLMMs will follow the framework of equation (1) above, however, for the underlying distribution of count outcomes we will assume a Poisson (or negative binomial, as appropriate) distribution with a log (as opposed to logit) link function. We anticipate a similar modeling approach for quantitative analyses of the impact of care coordination type on patient-reported outcomes (again adapting assumptions of the underlying distribution and corresponding link function, specific to the nature of each outcome variable). The main exception will be that we will not have baseline values for patient-reported measures, given that they will only be collected at a single time point in follow-up. Reporting of medical costs as a secondary outcome will follow PCORI standards.⁵³

Primary results for Aim 1 analyses will be reported as odds ratios, rate ratios, or (beta) differences (comparing the medical/social care coordination model to the nursing/medical model), with 95% confidence intervals, for each study outcome.

All Aim 1 analyses as described above will be replicated for both the Primary and Historical cohorts, and reported separately. To evaluate whether cohort-specific estimates statistically differ with respect to a given outcome, we will estimate pooled (Primary + Historical) models and evaluate the significance of the Wald test for the interaction term (*Cohort*CC Type*). Additionally, for the Historical cohort, care quality and utilization outcomes may potentially be available for up to 3 years from the onset of care coordination. Where data is available, we will estimate the impact of care coordination type on 1-year, 2-year, and 3-year outcomes respectively, using the framework described above, within the Historical cohort.

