7.3.3 Aim 3 Analysis

Identification of significant organization, care process, and patient factors will be embedded in analyses for Aims 1 and 2 and will be represented as covariates in final selected models for study outcomes. Whereas Aim 1 analyses seek to quantify effect estimates for $\gamma_{010}CC_{jk}$ in equation 1 above, for Aim 3 we intend to quantify γ coefficients for patient-level factors X , clinic-level factors W , and organization-level factors Z . As described above, we will iteratively optimize models using a forward stepwise selection algorithm. Summaries for unadjusted and adjusted comparisons for all variables under study will be tabulated and/or plotted accordingly. Again, Aim 3 analyses will be conducted separately for the Primary and Historical cohorts as described above.

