Directed acyclic graphs (DAGs) are the epidemiologist’s primary tool for specifying an underlying causal model, its key assumptions, and potential sources of bias.⁵⁴⁻⁵⁶ Briefly, DAGs are visual representations consisting of nodes (variables or vectors) and arrows (causal relationships, or more appropriately, lack of evidence that two variables are not causally related). They are ‘directed’ in that they depict unilateral

temporal sequences (typically left to right), and ‘acyclic’ in that circular pathways cannot be included (variables cannot cause themselves). We envision that our proposed quality measure and utilization outcome models could be represented by the following DAG, where \mathbf{A} is the care coordination model a patient receives (medical/social or nursing/medical), \mathbf{Y} is a specific study outcome (quality measure or utilization measure), \mathbf{Z} is the clinic-level decision to implement one care coordination model over the other, \mathbf{L}_c and \mathbf{L}_p are vectors of measured prognostic factors at the clinic and patient level, respectively, and \mathbf{U}_c and \mathbf{U}_p are vectors of unknown or unmeasured factors at the clinic patient levels, respectively.

We are interested in quantifying $\mathbf{A} \rightarrow \mathbf{Y}$. Estimates for this relationship can be biased when there are alternative ‘backdoor’ paths from \mathbf{A} to \mathbf{Y} . In this case, we can identify multiple backdoor paths via \mathbf{L}_c , \mathbf{L}_p , \mathbf{U}_c , or \mathbf{U}_p . By conditioning on measured covariates (e.g., including them in multivariable models), we can block backdoor pathways through \mathbf{L}_c and \mathbf{L}_p . Assuming the DAG is correct, we are then susceptible to bias only through unmeasured confounders \mathbf{U}_c or \mathbf{U}_p (to the extent they exist). To address this possibility, we will attempt to identify any relevant confounders that are undocumented in the data, and calculate e-values to determine if said confounder(s) could have plausibly accounted for the observed association.⁵⁷ For analyses of patient reported outcomes (via survey), we modified the previous DAG as follows:

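### Stepwise selection beyond an unlisted forced set does not guarantee the adjustment for measured confounders that the causal section assumes, and it distorts weak selected factors in Aim 3

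*Combined protocol and SAP*

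**What the plan says.** Section 7.3.1 builds each Aim 1 model in two steps. Investigators choose covariates that must be included, drawing on substantive knowledge, empirical evidence and fit statistics, with BIC given as an example. From there "a forward stepwise selection algorithm will select additional covariates to include until a stopping criterion is met". The forced set is not listed, the stopping criterion is not named, and the final model is specific to each outcome. The care-model effect is reported from that model with a 95% confidence interval. No allowance for selection is described.

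Section 7.3.6.1 argues that conditioning on the measured clinic and patient factors closes their backdoor paths, so that "we are then susceptible to bias only through unmeasured confounders".

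Other sections bear on which covariates count:
- Section 7.3.6.4 requires covariates measured at or before baseline and refers to 7.3.6.1 for how confounders are specified.
- Section 7.3.6.5 rules out propensity scores for primary analyses and leaves remaining imbalance to covariate adjustment.
- Section 7.3.8 uses experts and DAGs to identify confounders and examines imbalance by care model.

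For Aim 3, Section 7.3.3 states: "Identification of significant organization, care process, and patient factors will be embedded in analyses for Aims 1 and 2". It adds that "we will iteratively optimize models using a forward stepwise selection algorithm", and promises unadjusted and adjusted summaries for all variables studied.

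**The concern.** The causal argument and the model-building rule do not guarantee the same analysis. A forward step admits a covariate when it improves the fit to the outcome enough. Confounding bias depends on the product of two links: covariate to outcome, and covariate to care model. A clinic factor with a modest outcome link can miss the entry bar while still differing between care models, and its path then stays open although it was measured. Several such factors can add up. Because primary analyses use no propensity score, the covariate set carries all the control of measured confounding. The planned e-values address unmeasured confounders, not measured ones that selection left out.

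Aim 3 has a second problem. A factor that enters because its estimate happened to be large is then reported with that estimate and an ordinary interval. For weak factors this exaggerates the effect and can reduce coverage.

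At stake are the centring of the Aim 1 intervals, including those for primary outcomes, and the reliability of the Aim 3 list.

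**Working it through.** **Inputs from the plan (Section 7.2.1).** "we will recruit about 397 clinics"; "55% with a nursing/medical and 45% with medical/social care coordination model"; two-sided alpha 0.05 "with 80% power and an intra-cluster correlation of 0.01". About 10 survey patients per clinic at full recruitment, or 14 at 75%. PROMIS-10 SD 10, claimed detectable difference 1 point. PROMIS-10 is used because it is the outcome for which the text gives an SD. The plan gives no figure for selection bias.

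**Step 1: reproduce the plan's figure.** The design effect is 1 + (10 − 1) × 0.01 = 1.09. Effective sizes are 397 × 0.55 × 10 / 1.09 = 2,003 and 397 × 0.45 × 10 / 1.09 = 1,639. SE = 10 × √(1/2,003 + 1/1,639) = 0.333. Detectable difference = (1.960 + 0.842) × 0.333 = **0.93 points**. At 75% of clinics with 14 patients each it is also 0.93. The 1-point statement therefore reproduces for both survey scenarios in the text. (75% of clinics with 10 patients each gives 1.08.)

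**Step 2: how high is the entry bar?** With total variance 100 and ICC 0.01, a clinic mean of 10 patients has variance 1 + 99/10 = 10.9. The coefficient of a standardised clinic covariate has SE about √(10.9/397) = 0.166. An effect of 0.3 points per SD has expected z = 0.3/0.166 = 1.8, and 0.4 points has expected z = 2.4. Entry requires:
- AIC: |z| > √2 = 1.41
- p<0.05: |z| > 1.96
- BIC, n = 397 clinics: |z| > √ln 397 = 2.45
- BIC, n = 3,970 patients: |z| > √ln 3,970 = 2.88

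Confounders of this size will often miss every bar except AIC's.

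**Step 3: what does missing them cost?** A covariate correlated 0.15 with a 45/55 binary factor differs between care models by 0.15/√(0.45 × 0.55) = 0.30 SD. At 0.3 points per SD that is 0.09 points of bias. Five in the same direction, all omitted, give 0.45 points, or 1.4 standard errors of the care-model contrast.

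**Step 4: simulation.** 397 clinics × 10 patients, analysed as clinic means (equivalent to a random-intercept linear model with equal clusters), true care-model effect zero, 20 candidates, 2,000 runs. Confounder number and strength are assumptions, and all bias in the same direction. Type I error (%) of the care-model test:

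| Confounders left to selection | All forced in | AIC | p<0.05 | BIC, clinics | BIC, patients |
|---|---|---|---|---|---|
| None | 4.2 | 4.5 | 4.4 | 4.4 | 4.2 |
| 5, corr. 0.15, 0.3 pt/SD | 5.0 | 6.6 | 8.8 | 14.2 | 18.2 |
| 5, corr. 0.20, 0.3 pt/SD | 4.5 | 8.0 | 13.2 | 20.8 | 28.8 |
| 5, corr. 0.20, 0.4 pt/SD | 5.1 | 7.2 | 11.0 | 19.4 | 30.0 |
| 10, corr. 0.15, 0.3 pt/SD | 4.7 | 10.7 | 20.8 | 35.7 | 49.7 |

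The Monte Carlo standard error near 5% is √(0.05 × 0.95/2,000) = 0.5 percentage points. In the second row the mean spurious effect was 0.06, 0.16, 0.26 and 0.33 points across the four selection rules, all below the 0.45 of Step 3, as expected when some confounders do enter.

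With one confounder only (0.35 points per SD; correlation 0.2, 0.3, 0.5; 8,000 runs), type I error was 6.2%, 9.1% and 15.2% under BIC with n = clinics, and 5.6%, 7.9% and 12.6% under p<0.05.

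**Step 5: Aim 3, true factors that were selected.**

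| Rule | Overstated, 0.3 pt/SD | Overstated, 0.4 pt/SD | Naive 95% CI coverage |
|---|---|---|---|
| AIC | 1.34× | 1.14× | 95-97% |
| p<0.05 | 1.53-1.54× | 1.25× | 93-96% |
| BIC, clinics | 1.73-1.74× | 1.38× | 88-95% |
| BIC, patients | 1.92-1.93× | 1.51× | 79-91% |

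**Step 6: price of forcing the confounders in.** Under the five- and ten-confounder settings the variance inflation is about 1.12 to 1.23. √1.12 = 1.06 and √1.23 = 1.11, so standard errors rise 6-11%. The detectable difference moves from 0.93 to 0.93 × 1.06 = 0.99 and 0.93 × 1.11, about 1.04 points.

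**The case against.** The strongest reply is that the plan does attend to confounding by care model. Section 7 plans bivariate tests of patient, clinic and contextual factors against the comparator. Section 7.3.8 examines imbalance and uses experts and DAGs, and Section 7.3.6.5 sends remaining imbalance to covariate adjustment. The forced set is the natural home for what these steps find. This stands in part: a reader might infer that covariates are chosen with no regard to care model, and the documents do not support that. What is missing is the link. No section says that confounders so identified enter the forced set, and they are not listed.

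Second, a reader might take the error rates as a property of the plan. They are not. They need several real confounders, left outside the forced set and biasing the same way, and the highest need BIC, which the plan names only as an example. A separate run with six confounders (correlation 0.15, effects of 1 to 2.5 standard errors) gave 12-22% under BIC with n = 397 and 13-35% with n = 22,629 (397 × 57) when all pushed one way. With random signs these fell to about 7-12% and 7-13%. Under AIC it was 6-7% either way. This limits the size of the problem, not its existence.

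Third, a reader might infer that every Aim 3 factor is significant by construction. That fails for forced covariates, which are also Aim 3 factors. It fails under AIC as well, where only 34-63% of survivors had p<0.05 (100% under BIC, about 99% under p<0.05). Aim 3 is worded as exploration, and summaries are promised for all variables, not only survivors.

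**Conclusion.** The point holds in a conditional form. Section 7.3.1 does not secure the conditioning on which Section 7.3.6.1 relies, and the sections on identifying confounders do not close the gap. If confounders are left to selection, the care-model test can exceed 5%. With five assumed weak confounders (correlation 0.15-0.20, 0.3 points per SD, same direction) it was roughly 7-8% under AIC, 9-13% under p<0.05 and 14-29% under BIC. Inflation was nil when the confounders were forced in or absent, and small with a single weakly correlated one. For Aim 3, weak factors admitted by BIC or p-value rules were overstated about 1.3 to 1.9 fold, less as the true effect grew, and their naive intervals could under-cover.

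These sizes rest on assumed confounder strengths, equal clusters and a linear outcome. The logistic and count models were not simulated. The direction of the problem does not depend on those choices, but its actual size depends on what the unlisted forced set contains.

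**What to change.** - **Aim 1.** Base the primary estimate on one fixed adjustment set per outcome domain. It should contain every baseline patient, clinic and organization variable that the DAG and the experts identify as a confounder, chosen without reference to outcome fit. List it in Section 7.3.1 and cross-refer from 7.3.6.1, 7.3.6.4 and 7.3.8. The DAG is described in terms of vectors of factors, so the individual variables must be named.
- **Stepwise selection.** Keep it as a sensitivity analysis with its stopping rule stated, including which n is used if the rule is BIC.
- **Aim 3.** Report coefficients from the full fixed model, or use selection-adjusted intervals such as bootstrap intervals. Label the results exploratory.

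Selecting covariates in the Historical Cohort and estimating in the Primary Cohort is not a workable substitute. Patient-reported outcomes are collected for the Primary Cohort only (Section 7.3.6.2), and Aim 1 is to be estimated in both cohorts (Section 7.3.1).

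The cost is SAP wording, no new data, and the precision loss in Step 6. At the upper end of that loss the PROMIS-10 detectable difference slightly passes the plan's 1 point, so the power statement should be restated with the chosen set.

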7.1 Outcomes

Our outcomes fall into three categories: care quality (drawing on statewide quality measures reported by MNCM), utilization (drawing on insurance claims data collected by payor partners), and patient-centered/patient-reported outcomes (collected directly from care coordination patients who agree to complete a survey). Section 5 describes how data will be collected. **Table 3** summarizes study outcomes. Timing of outcome assessment will be anchored by the first date of receiving care coordination services, thereby creating a consistency across comparators and mitigating potential sources of bias due to timing. Modifications to these definitions and planned analysis may arise if certain data quality and availability thresholds are not met.

Table 3: Study Outcomes

Outcome measure	Definition	Source	Primary/ Secondary	Follow-up duration

Care Quality from the healthcare professional perspective				
Overall care quality	Composite measure of overall quality comprised of the percentage of all care quality outcomes in which a patient qualifies and meets quality criteria for	MNCM quality measures	Primary	12m
Asthma care at goal*	Asthma pts. with asthma control test (ACT) score >19	MNCM quality measures	Secondary	12m
Breast Cancer Screening* (up-to-date)	Women 50-74 yrs old who received a mammogram in the past one year	Health plan claims	Secondary	12m
Chlamydia Screening* (up-to-date)	Female patients 16-24 yrs old who had a screening test for chlamydia	Health plan claims	Secondary	12m
Colorectal Cancer Screening* (up-to-date)	50-75 yr old pts. up-to-date for an approved screening test	MNCM quality measures	Secondary	12m
Depression improvement*	PHQ-9 score <5 for test nearest to end of follow-up period	MNCM quality measures	Secondary	12m
Diabetes care at goal (including component measures)	All-in-one measure of control A1c, blood pressure, statin use, & smoking	MNCM quality measures	Secondary	12m
Vascular care at goal (including component measures)	All-in-one measure of control of blood pressure, statin use, & smoking + aspirin use in patients with vascular disease	MNCM quality measures	Secondary	12m
A1c control*	Hemoglobin A1c ≤ 7% in patients with diabetes	MNCM quality measures, clinic data	Secondary	12m
A1c level	Hemoglobin A1c in patients with diabetes	MNCM quality measures, clinic data	Secondary	12m

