Aspirin or anti-platelet use*	Aspirin use in patients with vascular disease unless with contraindication or exception	MNCM quality measures	Secondary	12m
Blood pressure control*	< 140/90 mm Hg	MNCM quality measures, clinic data	Secondary	12m
Blood pressure level	Systolic and diastolic blood pressure (mm Hg)	MNCM quality measures, clinic data	Secondary	12m

Body mass index	kg/m ² (Primary Cohort only)	MNCM quality measures, clinic data	Secondary	12m
Low-density lipoprotein level	mg/dL in patients with diabetes or vascular disease	MNCM quality measures	Secondary	12m
Statin use*	Current statin use in patients with vascular care unless with contraindication or exception	MNCM quality measures	Secondary	12m
Tobacco use*	Current tobacco use (tobacco includes any number of cigarettes, cigars, pipes, or smokeless tobacco) in patients with diabetes or vascular disease	MNCM quality measures	Secondary	12m
Utilization from the healthcare system perspective				
Emergency dept. visits	# of encounters with CPT-4 E&M codes (99281-99288) at emergency dept. site	Health plan claims	Primary	12m
Hospitalizations	# of hospital inpatient admissions ≥ 1 days	Health plan claims	Primary	12m
Hospital readmissions <30 days	# of hospital inpatient admissions ≥ 1 days following a prior hospitalization <30 days	Health plan claims	Secondary	12m
Primary care visits	# of encounters with CPT-4 E&M codes (99201-99215, 99381-99429) at primary care site	Health plan claims	Secondary	12m
Specialty care visits	# of encounters with CPT-4 E&M codes (99201-99215, 99381-99429, 99241-99245, 92920-93895) at primary care site	Health plan claims	Secondary	12m
Urgent care visits	# of encounters with CPT-4 E&M codes (99201-99215, 99381-99429) at urgent care site	Health plan claims	Secondary	12m
Substance use treatment	Substance use treatment indicated by HCPCS codes (H0005-H0029, H0047, H2034-H2036)	Health plan claims	Secondary	12m
# of chronic medications	# of distinct concurrent dispensed medications, combined across drug classes used for chronic conditions (e.g., hypertension, hyperlipidemia, diabetes, asthma, depression)	Health plan claims	Secondary	12m

Cost of medical care	Resource use x price index	Health plan claims	Secondary	12m
Patient reports from the patient/family perspective				
General health status	NHIS	Patient survey	Primary	6m-18m
Rating of primary care clinic	CG-CAHPS	Patient survey	Primary	6m-18m
Access to care	CG-CAHPS	Patient survey	Secondary	6m-18m

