- **Time in Care Coordination:** The study is intended to include patients who were enrolled in care coordination and engaged for a meaningful period of time, using whatever criteria make the most sense in your care system. Please do not include patients who were temporarily or “partially” enrolled. For example, some medical groups may apply an inclusion criterion to their query such as: include only patients who were enrolled for at least 2 months with at least 3 care coordination encounters within the care system. You may also use other ways to narrow the list to those enrolled patients intended for the study, depending on what parameters are used to define a “fully enrolled” care coordination patient in your system.

➤ **Exclusions:** Please apply any appropriate research exclusion lists to exclude patients who have opted out of research in your organization.

Summary of Changes for Primary Cohort

We had hoped to have few changes for this data submission but concluded that expanding the number of data points for three quality measures to include the following data would greatly improve the ability to measure changes in care quality from care coordination. If you have any questions or concerns about adding these data, please contact [contact].

- File 3: All HbA1c tests obtained during the specified time period (see below).
- File 4: All blood pressures obtained during the specified time period (see below).
- File 5: All height and weight values obtained during the specified time period (see below). Used for calculating BMI.

Questions? Please visit the [MNCARES Information Page](#) for answers to common questions or contact us at [contact].

Data Elements & Field Specifications – Files 1-5

File 1: Patient Demographic, Care Coordination Enrollment, Encounter Data

Element Order	Field Name	Details	Required or Situational*	Format/Field Length	Error Causes
A	Patient ID	Enter the patient ID that is submitted for clinical quality data submission to MNCM. If your clinic has not submitted MRNs or a unique patient ID in past submissions, please contact [contact] 
• Unique patient identifier for clinic.• DO NOT enter an SSN.	R	String; up to 50 characters	Blank fields
B	Patient First Name	Enter the first name of the patient.	R	Text	Blank fields
C	Patient Middle Name	Please enter the patient's middle name or initial if it is recorded in the medical record.	S	Text	

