Situational data is submitted if the clinic collects and can extract or obtain the information from their record system. Submit data for those patients when the information is available (e.g., secondary phone number). If the data was not collected or is not obtainable, the field can be left blank.

File 5 (Primary Cohort only): Height and Weight

Contains all heights and weights obtained or documented in the medical record from 01/01/2020 through the date of the data pull. One height and weight per row.

Element Order	Field Name	Details	Required or Situational*	Format/Field Length	Error Causes
A	Patient ID	Enter the Patient ID that was submitted in File 1. 
 • Unique patient identifier for clinic. • DO NOT enter an SSN. 	R	String; up to 50 characters	Blank fields
B	Encounter Date	Enter the date of the encounter where height/weight was obtained by clinical staff.	R	mm/dd/yyyy or m/d/yyyy	Blank fields
C	Height	Enter the value of the patient's height (inches, including decimals if applicable).	S	Number	
D	Weight	Enter the value of the patient's weight (pounds, including decimals if applicable).	S	Number	

* Both Required (R) and Situational (S) data are relevant to and important for the study. Required data must be submitted and cannot be blank.

Situational data is submitted if the clinic collects and can extract or obtain the information from their record system. Submit data for those patients when the information is available (e.g., secondary phone number). If the data was not collected or is not obtainable, the field can be left blank.

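### The only model given for individual care quality outcomes is binary within baseline-goal subgroups; it does not fit the four level outcomes in Table 3 (A1c, blood pressure, LDL, BMI), for which no continuous, baseline-adjusted model is stated.

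*Combined protocol and SAP*

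**What the plan says.** Table 3 (Section 7.1) places four level measures in the Care Quality block, all secondary: A1c level, blood pressure level, BMI (Primary Cohort only) and LDL level. A1c level is defined as "Hemoglobin A1c in patients with diabetes", with no cut-off. A1c control and blood pressure control are separate rows with thresholds. LDL and BMI have units but no goal.

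Section 7.3.1 states the rule: "Patient care quality outcomes for Aim 1 analyses will be modeled as binary dependent variables (e.g., meeting goal vs. not meeting goal) within subgroups" formed by the patient's status when care coordination began. Equation (1) is then written on the log-odds scale. One care quality outcome is treated differently. The composite gets a linear or tobit model with its baseline value as a covariate. Utilization outcomes get logistic and count models, and for patient-reported outcomes the distribution and link are to be adapted to each variable. The level outcomes are not mentioned.

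Appendix A (Section 17.1) extends the Primary Cohort submission to all A1c tests, blood pressures, heights and weights, because this "would greatly improve the ability to measure changes in care quality from care coordination". The height and weight file, for example, "Contains all heights and weights obtained or documented in the medical record from 01/01/2020 through the date of the data pull". That is a year before the first Primary Cohort start.

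**The concern.** The level outcomes have no model that fits them. Under the stated rule, A1c level and blood pressure level have to be cut at a threshold and so reproduce the control outcomes already listed. LDL and BMI cannot be analysed at all, because nothing defines meeting goal.

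If the analyst departs from the rule, the plan does not say what replaces it: a final value, a change score, an analysis adjusted for baseline or a dichotomised one, and in which patients. That choice would be made with the data in hand, alongside forward stepwise covariate selection.

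Precision is also at stake. Serial values were requested in order to measure change, but the written model uses the baseline only as above or below goal and discards the size of the follow-up value.

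**Working it through.** **Inputs from the documents (Section 7.2.1).** The plan's power work was done "assuming two-sided tests ($\alpha=0.05$) with 80% power and an intra-cluster correlation of 0.01". It says "we will recruit about 397 clinics", "55% with a nursing/medical and 45% with medical/social care coordination model", with 57 patients per clinic on average.

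**Inputs not in the documents, so assumed.** Pre-post correlation ρ 0.3-0.7; share at goal p 50-80%; bivariate normal values with the same cut-off at both times; in step 3, 20-30% of patients eligible for a given level outcome.

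**Step 1: the plan's own figure.** No power is stated for the level outcomes. The nearest continuous outcome with full inputs is PROMIS-10 (1 point, SD 10). Detectable difference = 2.80 × 10 × √[1+(m−1)×0.01] × √[1/(0.55·C·m) + 1/(0.45·C·m)].
- 397 clinics, m = 10: 0.93.
- 75% of 397 clinics, m = 14: 0.93.

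The 1-point claim is reproduced at the planned survey sizes, so the inputs are read as the plan intends.

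**Step 2: binary within subgroups against baseline-adjusted linear, clustering ignored.** Per-patient information for a small mean shift, in SD units:
- Linear, adjusted for baseline level: 1/(1−ρ²).
- Binary within one baseline subgroup: w·f²/[q(1−q)], where w is the subgroup's share of patients, q its probability of being at goal at follow-up, and f its follow-up density at the cut-off.
- Both subgroups combined: the sum of the two.

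Power = Φ(2.80·√RE − 1.96), where RE is the ratio to the linear model's information and the linear model has 80% power.

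Worked case, p = 0.6 and ρ = 0.5:
- Linear: 1/(1−0.25) = 1.333.
- At goal at baseline: q = 0.732, f = 0.359; 0.6×0.359²/(0.732×0.268) = 0.395; RE 0.30; power 33%.
- Not at goal: q = 0.402, f = 0.427; 0.4×0.427²/(0.402×0.598) = 0.303; RE 0.23; power 27%.
- Combined: RE 0.52; power 53%.

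Combined power over the grid (linear model 80% throughout):

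| At goal | ρ = 0.3 | ρ = 0.5 | ρ = 0.7 |
|---|---|---|---|
| 50% | 58% | 54% | 45% |
| 60% | 57% | 53% | 44% |
| 70% | 54% | 49% | 41% |
| 80% | 47% | 43% | 35% |

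Combined RE runs from 0.32 to 0.60. A single subgroup has RE 0.11-0.36 and power 15-39%. A separate simulation (ρ = 0.5, 50-69% at goal) gave 20-35% per subgroup and 48-53% for one binary model adjusted for baseline goal status, which agrees.

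**Step 3: planned size, with clustering.** Take 397 clinics, ICC 0.01, 30% of 57 = 17.1 eligible patients per clinic, ρ = 0.6 and p = 0.65. Variance = (0.01 + 1/(I·17.1)) × [1/(0.55×397) + 1/(0.45×397)], with I the information from step 2.

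| True shift | Linear, adjusted | Combined binary | At-goal subgroup | Not-at-goal subgroup |
|---|---|---|---|---|
| 0.075 SD | 93% | 69% | 49% | 37% |
| 0.15 SD | 100% | 100% | 97% | 90% |

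With 20% eligible, the 0.15 SD row becomes 100%, 98%, 89% and 77%.

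**The case against.** The fair reply is that the binary rule was never meant for the levels. Section 7.3.1 calls equation (1) a general form and illustrates it with at-goal examples. Table 3 keeps level and control apart, Section 7 promises a generalized linear mixed model for each outcome, and results may be reported as beta differences. This is a reasonable guess at intent. It still leaves the model, the baseline value and the analysed patients unstated, and beta differences are needed for the composite anyway.

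Three stronger readings are tempting and are not supported:
- *Baseline levels are never adjusted for.* They are unspecified, not excluded. Covariates are outcome-specific, and Sections 7.3.6.1 and 7.3.6.3 say the preceding 12 months will be taken into account. Section 7.3.1 treats the lack of a baseline as special to patient-reported outcomes. Splitting by baseline goal status is itself a coarse adjustment.
- *The extra clinic data are wasted.* Table 3 names clinic data as a source for A1c control and blood pressure control too, so dated readings help classify goal status around each start date. Only for height and weight is there no listed control outcome to serve.
- *Most of the power is lost.* That fits a single subgroup tested alone. With subgroups combined, a linear model's 80% falls to about 35-58%, although Section 7.3.1 describes no combining step.

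The objection also stands in that the size of the loss rests on assumed inputs and that no primary outcome is affected.

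**Conclusion.** The point holds as a mismatch between the stated rule and four secondary outcomes. For A1c and blood pressure level the rule duplicates existing outcomes; for LDL and BMI it cannot be fitted. This part needs no assumptions.

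The loss of precision is conditional. Under the assumed correlations and shares at goal, a literal binary analysis keeps about 32-60% of the information with subgroups combined and 11-36% in one subgroup. For a shift near 0.15 SD at full recruitment and 30% eligibility, little power is lost. For smaller shifts such as 0.075 SD the loss is material. The plan should be corrected, but its primary conclusions do not depend on it.

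**What to change.** In Section 7.3.1, limit the binary-within-subgroup rule to outcomes defined in Table 3 as at goal or not, and add text such as:

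*A1c level, systolic and diastolic blood pressure level, LDL level and BMI will be analysed with a linear mixed model (identity link, structure of equation (1), clinic random intercept). The patient's baseline level is a forced continuous covariate, and the care-model coefficient is the adjusted mean difference. Baseline is the most recent dated value preceding enrolment where such values exist (Primary Cohort A1c, blood pressure, BMI), and otherwise the pre-start MNCM measurement-year value where available (LDL, Historical Cohort).*

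For the Primary Cohort this needs no new collection of A1c, blood pressure, height or weight. It has three costs.
- Patients with no baseline value are dropped or imputed, and the plan should say which.
- The serial files cover only the Primary Cohort and contain no LDL, so baselines elsewhere are coarser.
- The clinic files end at the data pull, within the 15 March to 15 May 2022 submission window. Anyone starting after 15 May 2021 therefore has less than 12 months in them, and the latest starters far less. Their follow-up must come from MNCM 2022 data where available. Appendix B includes 2022 but Section 5.1.2 lists only 2019-2021 for this cohort, so the two should be aligned. BMI is most exposed, because none of the MNCM measures described in Appendix B includes height or weight.
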